Attachment 8: International Staging system

Intern	International Staging System						
Stage	Criteria	Median Survival (months)					
I	Serum β_2 microglobulin <3.5 mg/L, serum albumin \geq 3.5 g/dL	62					
II	Not I or III ^a	44					
III	Serum β₂ microglobulin ≥5.5 mg/L	29					
^a There are 2 possibilities for Stage II:							

¹⁾ Serum β_2 microglobulin <3.5 mg/mL but serum albumin <3.5 g/dL, or

²⁾ Serum β_2 microglobulin 3.5 - 5.4 mg/L irrespective of the serum albumin

Attachment 9: The Family of antihistamine medications

The following antihistamines may be used for daratumumab pre-dose medication (including, but not limited to):

- Diphenhydramine
- Cetirizine
- Fexofenadine
- Loratadine
- Clemastine
- Dexchlorpheniramine
- Promethazine*
 - * The IV use of promethazine should be avoided.

CONFIDENTIAL – FOIA Exemptions Apply in U.S.

Attachment 10: Anticipated Adverse Events

Anticipated Event

An anticipated event is an adverse event (serious or non-serious) that commonly occurs as a consequence of the underlying disease or condition under investigation (disease related) or background regimen.

For the purposes of this study the following events will be considered anticipated events:

- Bleeding
- Bone diseases
- Hypercalcaemia
- Hyperuricemia
- Hyperviscosity syndrome
- Infection
- Renal failure or insufficiency

Reporting of Anticipated Events

All adverse events will be recorded in the CRF regardless of whether considered to be anticipated events and will be reported to the sponsor as described in Section 12.3.1, All Adverse Events. Any anticipated event that meets serious adverse event criteria will be reported to the sponsor as described in Section 12.3.2, Serious Adverse Events. Each anticipated event will be assessed by the investigator at the individual case level and if considered to be drug-related will undergo expedited reporting (if appropriate) as per applicable clinical trial legislation to Health Authorities and IRB/IECs. If an anticipated event is considered disease-related or not related to study drug the event will be exempt from expedited reporting.

To meet US regulatory clinical trial legislation, the sponsor will perform aggregate review of anticipated events as outlined below, and if determined to be drug-related will implement expedited reporting of these events to Health Authorities and IRBs/IECs. If an interim analysis of trial results leads to an unblinded, aggregate review of safety data by the study team, the sponsor may terminate the review of pre-specified anticipated events outlined above.

Safety Assessment Committee (SAC)

A Safety Assessment Committee (SAC) will be established to perform reviews of pre-specified anticipated events at an aggregate level. The SAC is a safety committee within the sponsor's organization that is independent of the sponsor's study team. The SAC will meet to aid in the recommendation to the sponsor's study team as to whether there is a reasonable possibility that an anticipated event is related to the study intervention based on a review of the aggregate data by arm.

Statistical Analysis

Details of statistical analysis of anticipated events, including the frequency of review and threshold to trigger an aggregate analysis of anticipated events will be provided in a separate Anticipated Events Safety Monitoring Plan (ASMP).

Attachment 11: Long-term Survival Follow-up – After Final CSR Analysis Until Final OS Analysis

After the final CSR analysis, wich will provide updates to the primary CSR analysis for both efficacy and safety, all subjects, regardless of whether they are still on study treatment and those who are in follow-up, will enter the long-term survival follow-up. The subjects who are receiving treatment at the time of the cut-off for the final CSR analysis will continue to receive study treatment per protocol. The following limited schedule is applicable for the long-term survival follow-up.

Dosage and Administration

Study treatment will be administered according to the regimen established prior to Protocol Amendment 9 (see Section 6).

Once the sponsor has notified investigators that the final CSR analysis has been achieved, subjects may continue study treatment until PD per investigator evaluation, unacceptable toxicity, withdrawal of consent, the investigator decides to stop treatment, the start of subsequent anticancer therapy, or study completion (Section 17.9.1), whichever comes first.

Efficacy Evaluations

For subjects continuing study treatment during the long-term survival follow-up, investigators should monitor and assess subjects for response to treatment or disease progression according to local institutional practice and make decisions if treatment should be continued based on benefit /risk evaluation. The assessments and outcome should be entered in the subject file/source notes.

Safety Evaluations

For subjects continuing study treatment during the long-term survival follow-up, local hematology laboratory assessments, chemistry laboratory assessments, and assessment of vital signs should still be performed in accordance with good clinical practice and as per local label of drugs administered to guide safe use of study treatment. These local results do not need to be entered in the CRF.

Safety Reporting

For subjects continuing study treatment during the long-term survival follow-up, serious adverse events that occur while the subject is receiving study drug or are within 30 days after the last dose of study drug, will be collected and reported to the sponsor's global medical safety database via serious adverse event reporting process as indicated by Sponsor or designee (see Section 12.3.2). Serious adverse events that occur between 30 days after the last dose of the study drug and the end of study should be reported using the same process if considered by the investigator to be related to study drug. All serious adverse events should also be documented in the subject file/source notes.

Pregnancy reporting should continue as described in Section 12.3.4. The pregnancy should be documented in the subject file/source notes.

During long-term survival follow-up, reporting of anticipated events (Attachment 10) is no longer performed.

Patient Reported Outcomes

For subjects continuing study treatment during the long-term survival follow-up, no PRO data collection will occur.

Sample Collection and Handling

For subjects continuing study treatment during the long-term survival follow-up, there will be no PK, immunogenicity, or biomarker (MRD) assessments during this treatment period. Any sample collection or test for safety or disease evaluation should comply with local institution practice and be documented in the subject files/source notes.

Case Report Form Completion

The clinical database will remain partially open during the long-term survival follow-up. For all subjects on study, whether continuing study treatment or those in survival follow-up, CRF pages to be completed are:

- subsequent therapies
- survival follow-up
- death information
- end of treatment disposition
- end of study disposition

For survival follow up, the information can be obtained via telephone contact, medical records indicating the subject visited the hospital (laboratory, consult for other specialty), public records for deaths, etc.

Follow-up Procedures

For subjects who discontinue treatment during the long-term survival follow-up and the subjects who were in follow-up at the time of final CSR analysis, end of treatment procedures (Section 9.1.4) are not applicable, except for HBV DNA monitoring in accordance with the local label. These monitoring data should be documented in files/source notes but not entered in the CRF.

Source Documentation

At a minimum, the source data collected should include: subject and study identification, study discussion, documentation of the informed consent process including the date of consent, dates of visits, serious adverse events, pregnancy information, safety monitoring of subject as per local institution practice, drug dispensing/return records, study drug administration information, subsequent therapies, survival follow-up and death information, reason for end of treatment and for end of study.

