6. DOSAGE AND ADMINISTRATION

In this protocol, the term "study drug" refers to daratumumab only (daratumumab IV or daratumumab SC), and "study treatment" refers to daratumumab, lenalidomide, and dexamethasone. Daratumumab is to be administered as described in the Time and Events Schedule. Each cycle is 28 days. The first visit of a cycle should be 4 weeks after the start of the previous cycle. The start of each cycle may occur ±3 days of the scheduled day in order to accommodate the schedule of the site or subject. Day 1 of subsequent cycles should be adjusted accordingly to maintain the 28-day cycle duration. In Cycles 1 through 6, weekly or bi-weekly daratumumab doses may be given within ±1 day of the scheduled day in order to accommodate the schedule of the site or subject. In all cycles, weekly dexamethasone doses may be given within ±1 day of the scheduled day in order to accommodate the schedule of the site or subject. Changes to within-cycle dosing should not impact Day 1 of the next cycle. Subjects will continue to receive study treatment according to the Time and Events Schedule until disease progression, unacceptable toxicity, or other reasons as listed in Section 10.2.

Subjects whose study treatment is delayed for more than 4 weeks (Cycle 1 to Cycle 6) or more than 6 weeks (Cycle 7 and beyond) should have study treatment discontinued, unless, upon consultation with the sponsor and the review of safety and efficacy, continuation is agreed upon.

A schematic of study treatment administration is provided in Figure 4.

[figure not shown]

Figure 4: Schematic Overview Study Treatment Administration

 On days when daratumumab is administered, dexamethasone will be administered to subjects in Arm B in the clinic and will serve as the treatment dose of steroid as well as the required pre-medication prior to daratumumab infusion.

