6.1. Daratumumab (Arm B Only)

6.1.1. Daratumumab Preparation

Daratumumab doses will be prepared on the day of the planned administration. Detailed instructions for preparation and administration of daratumumab will be supplied in the Site Investigational Product Procedures Manual (SIPPM) or equivalent document.

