6.2. Lenalidomide (Arm A and Arm B)

Lenalidomide will be self-administered at a dose of 25 mg PO each day on Days 1 through 21 of each 28-day cycle for subjects with creatinine clearance >50 mL/min. If creatinine clearance is between 30 and 50 mL/min, the dose of lenalidomide will be 10 mg every 24 hours. Once the creatinine clearance is >50 mL/min during the course of the treatment, lenalidomide can be increased to 25 mg. In both treatment arms, subjects will continue on lenalidomide until progression of disease or unacceptable toxicity. Subjects in Arm B who discontinued treatment with Rd at 24 months may re-start treatment with Rd as per Amendment INT-4.

On daratumumab administration days, it is recommended that lenalidomide should be administered either prior to or at the same time (preferred) as the premedications.

If a daily lenalidomide dose is missed, it may be taken if <12 hours have elapsed since the time that it should have been taken. If the next dose is scheduled to be taken within 12 hours, the missed lenalidomide dose should be skipped.

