For subjects still receiving study treatment during the long-term survival follow-up until end of study, serious adverse events will continue to be reported as detailed in Attachment 11 and Attachment 12.

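### Attachment 11 sets the late SAE reporting window by *study drug* (daratumumab only), which contradicts the body text for subjects still taking lenalidomide and dexamethasone

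*Protocol*

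**What the plan says.** Protocol Section 6 defines two terms. *Study drug* "refers to daratumumab only (daratumumab IV or daratumumab SC"; *study treatment* "refers to daratumumab, lenalidomide, and dexamethasone". Section 6.1 gives daratumumab to Arm B only. For lenalidomide, Section 6.2 says: "In both treatment arms, subjects will continue on lenalidomide until progression of disease or unacceptable toxicity". Section 6.3 has the same rule for dexamethasone. Under Attachment 11, subjects on treatment at the final CSR cut-off "will continue to receive study treatment per protocol".

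The Safety Reporting paragraph of Attachment 11 opens: "For subjects continuing study treatment during the long-term survival follow-up". The events it covers are "serious adverse events that occur while the subject is receiving study drug or are within 30 days after the last dose of study drug". Later SAEs, up to the end of the study, are reported only if the investigator considers them related to *study drug*. Attachment 11 does not redefine the term. Attachment 5 does, for its own pages only, where it means lenalidomide.

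The body text is broader. Section 12.3.2 says: "For subjects still receiving study treatment during the long-term survival follow-up until end of study, serious adverse events will continue to be reported". Sections 9.8 and 12.3.1 say the same in substance. All three refer to Attachments 11 and 12 for the detail.

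**The concern.** One sentence uses both defined terms: the population is set by *study treatment* and the window by *study drug*. A site that knows the Section 6 definitions could fairly read them as different things. The window then has no meaning in Arm A, where daratumumab is not part of assigned treatment.

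The paragraph matters because little else is left in this phase. Section 9.8 limits adverse event collection after the final CSR to SAEs. The CRF pages that Attachment 11 keeps open cover subsequent therapies, survival, death and the two disposition forms; none is for adverse events. The SAE route is therefore the sponsor's remaining channel for on-treatment toxicity. It includes second primary malignancies, which Section 12.1.1 names among medically important events. If sites apply the narrow reading, reports would be lost mainly from the arm that does not receive daratumumab.

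**Working it through.** No sample size, error rate or event count is involved, so the check is a comparison of texts.

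1. **Terms.** Section 6: *study drug* is daratumumab; *study treatment* is all three agents.
2. **Who can still be on treatment.** Both arms, because Rd continues until progression or unacceptable toxicity (Sections 6.2 and 6.3) and carries on past the cut-off (Attachment 11). Section 6.4 lets a subject stop one component and stay on the others, so Arm B may include subjects on Rd without daratumumab.
3. **Apply the Section 6 definition to the Attachment 11 window**, and compare it with a window set by the last dose of *study treatment*, which is how Section 12.3.1 words its own 30-day SAE sentence.

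| Group still on treatment | Attachment 11, with *study drug* as defined | Window set by *study treatment* |
|---|---|---|
| Arm B, on daratumumab | On daratumumab and 30 days after its last dose; then daratumumab-related SAEs only | On any component and 30 days after the last dose |
| Arm B, daratumumab stopped, Rd continuing | Closes 30 days after the last daratumumab dose although treatment continues; then daratumumab-related SAEs only | Same as above |
| Arm A, on Rd | No start or end can be derived | Same as above |

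4. **Late events.** After 30 days the test is relatedness to *study drug*. In either arm, an SAE attributed only to lenalidomide or dexamethasone fails it.
5. **Does the body text settle it?** Sections 9.8, 12.3.1 and 12.3.2 show that reporting is meant to continue for everyone on study treatment. But each sends the reader to Attachment 11 for the detail, and the general adverse event window in Section 12.3.1 ends when long-term survival follow-up starts. Section 12.3.2 also has a general duty to report every SAE during the study. That duty conflicts with the narrower Attachment 11 rule, and I found no statement of which prevails.
6. **A contrast.** Section 8.4 gives an explicit SAE window to Arm A subjects who receive sponsor-supplied daratumumab after progression. Arm A subjects still on randomised Rd have nothing equally clear.
7. **Attachment 12.** Its SAE rule is addressed to subjects continuing daratumumab, so *study drug* fits its stated population.

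**The case against.** The strongest reply is that the duty to report is intact. The general duty in Section 12.3.2 has no limit by arm or drug, and the Attachment 11 sentence itself cites that section. Sections 9.8 and 12.3.1 point the same way. A reading that empties the rule for one arm sits badly with its own opening words, which cover both. The protocol also uses *study drug* loosely: the adverse event row of the Time and Events Schedule covers both arms but runs to the last *study drug* dose, and the dose administration table lists lenalidomide and dexamethasone under a study-drug heading for both arms. Sites may well have read the term broadly throughout.

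Much of this stands, and it rules out several stronger inferences that a reader might draw:

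- **That Rd-arm SAEs have no reporting window at all.** This is true only of the Attachment 11 paragraph read with the Section 6 definition. It is not true of the protocol as a whole.
- **That sites would not report these events.** This predicts conduct, and assumes that sites ignore Section 12.3.2.
- **That unreported events are lost for good.** Attachment 11 requires all SAEs to be documented in the subject file, and its source documentation list includes them. What is at risk is prompt reporting to the sponsor.
- **That a planned comparison between arms is biased.** The planned safety update is the final CSR, which comes before this phase. The later addendum reports eCRF data, and SAEs in this phase go to the safety database.

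The reply does not remove the conflict. Loose usage elsewhere adds to the ambiguity, and the sections that state the intent hand the operative rule to the paragraph that fails to carry it out.

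**Conclusion.** The point holds as an internal contradiction. The Attachment 11 SAE paragraph does not work for two groups on treatment, Arm A on Rd and Arm B on Rd without daratumumab, when its own defined term is applied. It also leaves out late SAEs attributed only to lenalidomide or dexamethasone. The consequence is a risk of under-reporting that differs by arm, not a demonstrated absence of reporting.

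The size cannot be stated. The documents give 365 planned subjects per arm but no count or share still on Rd at the final CSR cut-off. A reader might assume a share, for example 5% to 15% (0.05 × 365 ≈ 18; 0.15 × 365 ≈ 55), but nothing in the documents supports those shares, and the result should not be cited as a finding.

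The conclusion assumes that Section 6 governs Attachment 11, which is the natural reading because Attachment 11 has no local definition.

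**What to change.** In the Attachment 11 SAE paragraph, replace *study drug* with *study treatment* at all four occurrences: while receiving it, within 30 days after the last dose, between 30 days after the last dose and the end of study, and related to it. Alternatively, add one sentence defining the term for that attachment, as Attachment 5 does. Either change brings the paragraph into line with Sections 9.8, 12.3.1 and 12.3.2. Attachment 12 needs no change.

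The cost is a wording change. Section 17.1 requires a formal amendment to modify the protocol; a clarification letter to sites could state the intended reading meanwhile. Expect a small number of additional SAE reports. No treatment rule, visit or analysis changes.

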Attachment 12: Final OS Analysis Until End of Study

Protocol Amendment 9 will allow those subjects who are benefitting from daratumumab treatment at the time of the clinical cut-off date for the final OS analysis to continue to receive daratumumab. The sponsor will ensure that subjects will be able to continue to receive daratumumab after the final OS analysis until the end of study (defined in Section 17.9.1). The following limited schedule is applicable.

Documentation of assessments performed is required only in the subject file/source notes.

Dosage and Administration

Daratumumab will be administered according to the regimen established prior to Amendment 9 (see Section 6).

Treatment Period

Once the sponsor has notified investigators that the clinical cut-off date for the final OS analysis has been achieved (end of eCRF data collection), subjects may continue treatment with daratumumab until PD per investigator evaluation, unacceptable toxicity, withdrawal of consent, the investigator decides to stop treatment, the start of subsequent anticancer therapy, or the end of the study (defined in Section 17.9.1). For subjects who continue treatment after the final OS analysis, post-treatment follow-up is not applicable, except for HBV DNA monitoring in accordance with the local label.

Efficacy Evaluations

Investigators should monitor and assess subjects for response to treatment or disease progression according to local institutional practice. The assessments and outcome should be entered in the subject file/source notes.

Safety Reporting

For subjects continuing daratumumab after the clinical cut-off date for the final OS analysis, serious adverse events that occur while the subject is receiving study drug and within 30 days after the last dose of study drug will be collected and reported to the sponsor's global medical safety database only via the same serious adverse event reporting process used over the course of the study. Serious adverse events that occur between the 30-day post-dose period and completion of the study should be reported using the same process if considered by the investigator to be related to study drug. Serious adverse events should also be documented in the subject file/source notes.

Pregnancy reporting should continue as described in Section 12.3.4. The pregnancy should be documented in the subject file/source notes.

Sample Collection and Handling

VGPR very good partial response

WBC white blood cells

1. INTRODUCTION

This statistical analysis plan (SAP) contains definitions of analysis sets, derived variables, and statistical methods for the planned analyses as specified in the protocol JNJ-54767414MMY3008, Amendment INT-4.

1.1. Overview of Trial Design

This is a randomized, open-label, active controlled, parallel-group, multicenter study in subjects at least 18 years of age with previously untreated multiple myeloma who are not candidates for high dose chemotherapy and ASCT. The primary objective is to evaluate if daratumumab in combination with Rd prolongs progression-free survival (PFS) compared with Rd alone. The secondary objectives are to compare the 2 treatment groups with respect to time to disease progression (TTP), complete response (CR) or better rate, MRD negativity rate, progression-free survival on next line of therapy (PFS2), overall survival (OS), time to next treatment, overall response rate (ORR), very good partial response (VGPR) or better rate, sCR rate, time to response, duration of response as well as to assess the safety and tolerability of daratumumab when administered in combination with Rd.

Approximately 730 subjects will be randomized in this study with 365 subjects planned per treatment arm (DRd or Rd). Randomization will be stratified by International Staging System (I vs II vs III), region (North America vs Other), and age (<75 vs ≥75). Within each stratum, subjects will be randomized using an equal allocation ratio of 1:1.

Subject participation will include a Screening Phase, a Treatment Phase, and a Follow-up Phase. The Screening Phase will be up to 21 days before Cycle 1 Day 1. The Treatment Phase will extend from Day 1 of Cycle 1 until discontinuation of all study treatment. For subjects assigned to DRd, daratumumab will be administered weekly for the first 8 weeks (Cycles 1-2) of treatment and then every other week for 16 weeks (Cycles 3-6), then every 4 weeks (from Cycle 7 and beyond) until disease progression or unacceptable toxicity. This will equate to 9 consecutive weeks of dosing at the start of the study and a total of 23 doses in the first year. Lenalidomide will be administered at a 25 mg or 10 mg orally (PO) on Days 1 through 21 of each 28-day cycle, and dexamethasone will be administered at a dose of 40 mg or 20 mg once a week for both treatment arms (per age, for more detail refer to protocol Section 6. Dosage and Administration). Those in the Rd arm will receive lenalidomide will be administered at a dose of 25 mg or 10 mg orally (PO) on Days 1 through 21 of each 28-day cycle, and dexamethasone will be administered at a dose of 40 mg or 20 mg once a week until disease progression or unacceptable toxicity. Subjects in both treatment arms will continue lenalidomide and dexamethasone until disease progression or unacceptable toxicity. In the DRd arm, subjects will continue on daratumumab until disease progression or unacceptable toxicity.

The Follow-up Phase will begin once a subject discontinues all study treatments. Subjects who discontinue for reasons other than disease progression must continue to have disease evaluations according to the Time and Events Schedule which will continue until confirmed progression disease (PD), death, lost to follow up, consent withdrawal, subsequent anticancer therapy, or

study end, whichever occurs first. After the clinical cut-off (see below for definition), data collection will be reduced as per protocol Section 9.1.4.

Two interim analyses are planned (for detail refer to Section 1.4).

The primary PFS analysis will occur when approximately 390 PFS events have been observed. The date established for the primary PFS analysis will serve as the clinical cut-off date, after which data collection in the study will be reduced. Investigators will be informed when each interim analysis is to occur. All available data prior to that time will be included in each of the respective analyses.

The end of the study will occur when 330 subjects have died, or 7 years after the last subject is randomized, whichever comes first. The sponsor will ensure that subjects benefiting from treatment with daratumumab will be able to continue treatment after the end of the study.

An Independent Data Monitoring Committee (IDMC) will be commissioned for this study to review efficacy and safety results at the planned interim analyses (more detail information including the timing refer to section 1.4). After the interim reviews, they will make recommendations regarding the continuation of the study. In addition, the IDMC may also review cumulative safety data every 6 months besides the 2 interim analyses.

Assessment of tumor response and disease progression will be conducted in accordance with the International Myeloma Working Group (IMWG) response criteria. An assessment of MRD will be conducted on bone marrow samples. Safety evaluations will include adverse event monitoring, physical examinations, electrocardiogram (ECG) monitoring, clinical laboratory parameters (hematology and chemistry), vital sign measurements, and Eastern Cooperative Oncology Group (ECOG) performance status. Blood samples will be drawn for assessment of pharmacokinetic parameters.

